### *Methods*

Sixty patients following total knee arthroplasty will be monitored for up to 10 weeks during their outpatient physical therapy course. For the control group, 30 of these patients will undergo two to three weekly sessions with a physical therapist supplemented by unmonitored home-based exercises. The second group of 30 patients will fulfill their rehabilitation course with one to three sessions per week with a physical therapist and will use the interACTION home rehabilitation monitoring program to supplement these sessions. The patients in the interACTION group will use the device for the first two weeks of their rehabilitation in the clinic in order to become familiar with the device before home use. After the first two weeks the patient will be asked to take the device home and reduce their weekly outpatient visits by one visit per week. However, if the physical therapist feels it is best for the patient to deviate from the protocol, this is allowed. At the end of the 10-week rehabilitation course, rehabilitation compliance, costs, and patient outcomes will be analyzed for differences between the two groups.

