## **Methods**

For this randomized treatment study, we will recruit 60 patients that have undergone total knee arthroplasty (TKA) that are being referred for post-operative outpatient physical therapy. After obtaining informed consent, and upon successful

screening/recruitment, subjects will be randomly assigned to one of two groups:

1. Control Group: Rehabilitation performed by a physical therapist and supplemented with a home exercise program for a maximum of ten weeks. Therapy will consist of two to three visits per week as prescribed by the physical therapist and based on the best interest of the patient. Patients will record their performance of the prescribed home exercise programs on a paper-based exercise log on a daily basis.
2. InterACTION Intervention Group: Rehabilitation performed by a physical therapist and supplemented by use of interACTION for a maximum of ten weeks. This will include two to three visits per week for two weeks in which the patient will use interACTION during routine outpatient physical therapy sessions to familiarize them with the system. After two weeks, the patient will be issued an interACTION device for home use that will guide them through their exercise program. At this point subjects in the interACTION group should continue to return to the outpatient rehabilitation facility, but reduce their weekly routine visit with their physical therapist by one during the next eight weeks of recovery, while concurrently using interACTION at home. Patients who attended two visits per week for the first two weeks should subsequently attend one visit per week. Patients who attended three visits per week for the first two weeks will subsequently attend one to two visits per week. However, if the physical therapist feels it to be in the best interest of the patient to deviate from the protocol, this is allowed.

*Note: InterACTION is currently under development, not a commercial application. The 3rd Party Developer was OpenArc, LLC ([name]). The mobile application is currently supported on a Nexus tablet with Android operating system (specifically lollipop and kitkat versions). The mobile application and the kinematic sensors will be provided to the participant, the participants will NOT use a personal device.*

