Rehabilitation Compliance will be evaluated by the study team through the use of home exercise logs and interACTION reports. Logs will be reviewed at the follow-up visits with the research team. Outcome measures will be collected at baseline, 5 weeks (+/- 7 days) after enrollment, and upon discharge or a maximum of 10 weeks (+/- 7 days) after enrollment.

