#### *Statistical Analysis*

For the baseline data, continuous variables were compared with the two-sample t-test and categorical variables were compared with Fisher's exact test or a chi-square test.

For the primary outcome (value, ratio of ADLS to cost), the Wilcoxon rank sum test was used to compare between the Control Group and interACTION Group. P-Values below \* $p=0.05$  were considered statistically significant for all outcomes. For the remainder of the cost analyses parameters (weeks of physical therapy, number of physical therapy visits, and total cost), a two-sample t-test was used to compare between groups.

For other clinical outcomes data, if the distribution was normal at each time point, then a repeated measures ANOVA was used. A repeated measures ANOVA was used to compare difference between groups for the ADLS, Passive ROM (flexion), and Active ROM (flexion). Otherwise, if some time points had normal data and others did not then a two-sample t-test was used for normally distributed data and the Wilcoxon rank sum test was used for non-normally distributed data.

For the functional performance tests that were assessed at the 5- and 10-week visits, a z-score (or standard score) was used to calculate a cumulative score for the Six-minute Walk Test (distance in feet), Stair Climb Test (time divided by steps), TUG (time), and Surgical Unilateral Balance (time). The z scores are the average of the z scores for each of the functional tasks. On average, the z scores are close to zero, meaning that the overall individuals within the group, the scores for each subject are not different than the mean score across all subjects.

Differences between the cumulative z-scores were assessed using a two-sample t-test.

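### Repeated measures ANOVA in its classical form would leave out patients without all three ADLS or flexion ROM readings; a mixed model on all observed readings avoids this

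*Combined protocol and SAP*

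**What the plan says.** The Statistical Analysis section gives one condition for the method: "if the distribution was normal at each time point, then a repeated measures ANOVA was used". It then names the outcomes: "A repeated measures ANOVA was used to compare difference between groups for the ADLS, Passive ROM (flexion), and Active ROM (flexion". It names no model form, covariance structure or software.

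The Methods section sets the schedule: "Outcome measures will be collected at baseline, 5 weeks (+/- 7 days) after enrollment, and upon discharge or a maximum of 10 weeks", the last also with a 7-day margin. Therapy length is capped but has no minimum; for the control arm it is "supplemented with a home exercise program for a maximum of ten weeks", and the interACTION arm has the same cap. Duration is itself compared between arms, among the cost parameters "weeks of physical therapy, number of physical therapy visits, and total cost".

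The documents do not state how a missing reading is handled, which patients form the analysis set, whether a patient discharged before week 5 is still assessed then, or which time point an early discharge reading represents. They give no expected or observed rate of withdrawal or early discharge.

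**The concern.** A classical repeated measures ANOVA works on a full subject-by-visit table. If one of a patient's three readings is missing, either the whole patient is set aside, including the readings that were collected, or a value is filled in. The plan authorises neither, so the choice would be made after the data are in.

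The schedule makes gaps plausible. Someone discharged early may have a baseline and a discharge reading but nothing separate at 5 weeks. Someone who withdraws after week 5 lacks the final reading. The first is likely to be recovering well and the second may not be, so the patients lost need not resemble those kept. Because one arm makes fewer clinic visits and therapy length is a compared outcome, the pattern could also differ by arm. The comparison of ADLS and flexion ROM would then no longer be between the groups as randomised.

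**Working it through.** The plan states no power, dropout rate or SD, so there is no figure of its own to reproduce. All missing-data rates below are assumptions.

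**Inputs from the documents.** 60 patients (Methods), 30 of them control (Abstract), hence 30 per arm; three planned readings (Methods); significance level 0.05 (Statistical Analysis), taken as two-sided because sidedness is not stated.

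**1. Does the classical method need complete sets?** A standard classical routine was given artificial data for 6 subjects at 3 visits with one reading deleted. It stopped and reported unbalanced data. Incomplete patients must be removed or filled in before it will run.

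**2. Complete cases.** Let d be the proportion missing at each of the two post-baseline visits. With independent misses, complete cases = 60(1−d)². The standard error relative to no missing data is 1/√((1−d)²) = 1/(1−d). An analysis using every observed final reading has 60(1−d) of them, with relative standard error 1/√(1−d) if it gains nothing further from the correlation between visits.

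| d | complete cases | SE rise, complete cases | final readings observed | SE rise, observed final readings |
|---|---|---|---|---|
| 5% | 60 × 0.9025 = 54.2 | 5% | 57 | 2.6% |
| 10% | 60 × 0.81 = 48.6 | 11% | 54 | 5.4% |
| 15% | 60 × 0.7225 = 43.4 | 18% | 51 | 8.5% |

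On this reckoning about half of the SE rise remains under a mixed model, because it cannot restore readings never taken.

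Independence is only a convenience. If different patients miss the two visits, complete cases are 60(1−2d) = 54, 48 or 42. If the same patients miss both, they are 60(1−d) = 57, 54 or 51, and those patients have only a baseline to contribute.

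**3. Yardstick.** For one two-group comparison with 80% power, the detectable difference is (1.96 + 0.84)√(2/n) SD. With n = 30 per arm this is 0.72 SD. With 27, 24 or 21 per arm it is 0.762, 0.809 or 0.865 SD, and power at 0.72 SD falls from 80% to 76%, 71% or 65%.

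**4. Bias.** Simulation: 500 runs per scenario, 30 per arm, no true difference; correlations 0.6 (baseline and week 5), 0.5 (baseline and final) and 0.7 (week 5 and final). The best recoverers, judged by the final reading, have no week-5 reading. Complete cases are compared with a likelihood model, unstructured covariance, on all observed readings.

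| early discharge, control / interACTION | mean complete cases | bias in final difference, complete cases | bias, all observed |
|---|---|---|---|
| 10% / 10% | 54.2 | 0.01 SD | −0.01 SD |
| 20% / 20% | 48.0 | 0.01 SD | −0.01 SD |
| 5% / 20% | 52.6 | −0.24 SD | −0.01 SD |
| 10% / 30% | 48.1 | −0.30 SD | 0.00 SD |

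A closed form agrees. Removing the top fraction p of a standard normal leaves a mean of −φ(z)/(1−p), where z is the upper p point. For 5% / 20%: −0.280/0.80 + 0.103/0.95 = −0.350 + 0.109 = −0.24. For 10% / 30%: −0.348/0.70 + 0.175/0.90 = −0.497 + 0.195 = −0.30. Against the yardstick, 0.24/0.72 = 0.33 and 0.30/0.72 = 0.42. The arm with more early discharge looks worse than it is.

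**The case against.** The strongest reply is that the documents nowhere say incomplete patients are removed. The term repeated measures ANOVA is also used for mixed models fitted to all observed visits. This stands. A reader might infer that the plan drops every patient with a missing visit, but the text supports only that its named method does so in its classical form.

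Second, early discharge need not remove the 5-week reading. That visit is timed from enrollment, the Outcomes section plans 5- and 10-week functional tests for everyone, and nothing cancels week 5 after discharge. A discharge in week 4 or 5 can also fall inside the window. This stands as far as it goes, but one assessment might then have to serve as both the 5-week and the final reading, and no rule covers that.

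Third, the size is conjectural. The documents report no withdrawals or early discharges; the counts rest on assumed, independent misses; and complete-case bias was about zero when early discharge was equally common in both arms. All of this stands and limits the claim to a possibility.

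Fourth, a reader might infer that the primary result is compromised because ADLS enters the value ratio. It does not follow: that ratio is compared by a Wilcoxon rank sum test, and deletions inside the ANOVA do not reach it.

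What survives is that the named method, read in its ordinary sense, discards collected readings when sets are incomplete, the schedule makes incomplete sets plausible, and a better method is readily available.

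**Conclusion.** The point holds in limited form. As named, the analysis of ADLS and of passive and active flexion ROM could be confined to patients with all three readings. The resulting loss of precision is modest at the assumed rates: about 54 to 43 of 60 patients complete at 5% to 15% missing per post-baseline visit, with only part of the loss recoverable. Bias needs two further conditions, that losses are related to recovery and that they differ by arm. Under assumed early-discharge rates of 5% against 20%, or 10% against 30%, it reached 0.24 to 0.30 SD; under equal rates it was negligible. The actual rates are not given, so neither the size nor the presence of bias can be established from the documents. The matter concerns secondary analyses in a pilot study. It should be corrected, but it does not undermine the primary comparison.

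**What to change.** Replace the repeated measures ANOVA for these three outcomes with a likelihood-based linear mixed model: arm, visit and arm-by-visit as fixed effects, unstructured covariance over the three time points, fitted by REML. Use all observed readings, baseline included, of all randomised patients in the arm to which they were assigned. State in advance which time point a discharge reading represents when discharge comes before or within the 5-week window. If a mixed model of this kind is what the plan means, saying so and adding the discharge rule is enough.

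The section is written in the past tense. If the analysis has already been run, it can be re-run on the data in hand, with the discharge rule fixed without reference to the group results.

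The cost is a few sentences and different code, with no new patients or procedures. The downside is that validity rests on data being missing at random given the observed readings. That is weaker than what complete-case ANOVA needs, but it is still an assumption, and the model cannot replace readings that were never taken.

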### *Outcomes*

- Range of motion—Active and passive range of motion (ROM) will be measured with a standard goniometer while the patient lies in the supine position. Extension and flexion of each knee will be measured. Extension will be measured passively with a quad set and actively during a straight leg raise. The range of extension and flexion will be expressed as the difference between the involved and non-involved knees.
- Numeric Pain Rating Scale—Subjects will be asked to rate their level of pain currently and their level of worst & least pain in the past 24 hours on a scale from 0 (no pain) to 10 (worst pain imaginable).
- Activities of Daily Living Scale of the Knee Outcome Survey (ADLS)—The ADLS is a 14-item measure of symptoms and activity limitations for

individuals with a variety of knee impairments.

- Veterans RAND 12-Item Health Survey (VR-12)—The VR-12 is a 12-item patient-reported general measure of health-related quality of life that was adapted and developed from the RAND 36-Item Health Survey at the RAND Corporation and Medical Outcomes Study.
- Functional performance will also be tested in all patients. The following functional tests will be assessed at 5- and 10-week visits:
  - Six-minute Walk Test to assesses the subject's ability to walk community distances. The subject is asked to walk as far as possible in six minutes on a closed course with standing rest breaks as needed. The patient is free to use their preferred assistive device.
  - The Stair Climbing Test to test basic daily function in which a patient ascends and descends a standard flight of stairs as quickly and safely as possible, using their preferred gait pattern, assistive device, and hand rail.
  - The Timed Up and Go Test (TUG) in which the patient sits in a standard armed chair, rises, walks three meters, turns around, walks back to the chair and sits. Excessive time to complete the TUG can indicate mobility impairments and potential fall risks in elderly patients.
  - The Unilateral Balance Test in which the patient attempts to maintain single leg balance for up to two minutes, with the test ending when the patient loses balance enough to put the opposite foot on the ground.

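### The functional composite averages z-scores from tests that run in opposite directions, with no sign reversal stated, so a uniform benefit or harm cancels to zero

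*Combined protocol and SAP*

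**What the plan says.** The Statistical Analysis section says of the 5- and 10-week functional tests that "a z-score (or standard score) was used to calculate a cumulative score". The components are "Six-minute Walk Test (distance in feet), Stair Climb Test (time divided by steps), TUG (time), and Surgical Unilateral Balance (time"). The combination rule is one sentence: "The z scores are the average of the z scores for each of the functional tasks". The arms are then compared: "Differences between the cumulative z-scores were assessed using a two-sample t-test". Units are given for each component except the two plain times, but no component is given a direction, no reversal is mentioned, and the composite is not said to be better when higher or lower.

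The Outcomes section gives the directions of the individual tests:

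- **Walk test:** "The subject is asked to walk as far as possible in six minutes", so higher is better.
- **Stair test:** the patient "ascends and descends a standard flight of stairs as quickly and safely as possible", so lower is better.
- **TUG:** "Excessive time to complete the TUG can indicate mobility impairments and potential fall risks in elderly patients", so lower is better.
- **Balance test:** a timed single-leg stand, capped at two minutes, that ends when the other foot touches down, so higher is better.

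The only interpretive remark on the composite is that z-scores are near zero on average, which the plan takes to mean that "the scores for each subject are not different than the mean score across all subjects".

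**The concern.** Two of the four components rise with better function and two fall. A plain average of them does not measure overall function. It measures the contrast between walk and balance on one side and stair and TUG on the other. A treatment that helped, or harmed, all four tests equally would leave it unchanged.

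This composite is the analysis that the plan specifically assigns to the functional tests. The Potential Benefits section describes success as outcomes at least as good with fewer clinic visits. Under the rule as written, a uniform functional harm would appear as no difference, and a reader could take that as support for the claim. If the signs were in fact aligned, the plan does not say so, and a reader cannot tell which arm a positive difference favours.

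**Working it through.** **Inputs from the documents.** Four components, combined by unweighted average; test directions as listed above; two-sample t-test; significance threshold 0.05; 60 patients, 30 per group. The plan does not state sidedness, so two-sided is assumed. It gives no effect size, SD, correlation or power for this composite, so there is no stated figure to reproduce.

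**Algebra.** Let d be the benefit on each test in SD units, positive meaning better. The shifts on the measured scales are +d_walk, −d_stair, −d_TUG and +d_balance.

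- As written: (d_walk − d_stair − d_TUG + d_balance)/4. With all equal to d: (d − d − d + d)/4 = 0.
- Stair and TUG reversed: (d_walk + d_stair + d_TUG + d_balance)/4. With all equal to d: d.

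Put a = d_walk + d_balance and b = d_stair + d_TUG. When a and b share a sign, |a − b| ≤ |a + b|, so the score as written never shows a larger difference than the aligned one. If higher is read as better, a true benefit takes the wrong sign whenever b exceeds a. When a and b have opposite signs, the score as written can be inflated instead.

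**What the score measures.** Assume a common correlation ρ between tests on the benefit scale. Of the six pairs, two agree in direction and four disagree.

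- Variance as written = (4 − 4ρ)/16 = 0.175, 0.125, 0.075 at ρ = 0.3, 0.5, 0.7.
- Variance aligned = (4 + 12ρ)/16 = 0.475, 0.625, 0.775.
- Covariance of the two scores = (1 + 3ρ)(1 − 1 − 1 + 1)/16 = 0.
- Correlation with a single common function factor: aligned, √ρ/√((1 + 3ρ)/4) = 0.79, 0.89, 0.95; as written, 0.

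**Rejection rates.** Simulation with 20,000 replicates per cell, multivariate normal data, ρ from 0.3 to 0.7, 30 complete patients per arm, each test standardised on both arms together, two-sided t-test at 0.05. Monte Carlo standard error is at most 0.4 percentage points. Effects are assumed and listed as walk/stair/TUG/balance.

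| Effects (SD) | Difference as written | p<0.05 as written | Difference aligned | p<0.05 aligned |
|---|---|---|---|---|
| none | 0.00 | 4.9–5.1% | 0.00 | 4.8–5.0% |
| +0.5 on all | 0.00 | 4.0–4.3% | +0.48 | 57–79% |
| −0.5 on all | 0.00 | 4.0–4.4% | −0.48 | 58–79% |
| +0.8 on all | 0.00 | about 3% | +0.74 | 93–99% |
| 0.4/0.6/0.6/0.4 | −0.09 | 13–25%, wrong direction | +0.48 | 58–79% |
| 0.2/0.8/0.8/0.2 | −0.27 | 73–98%, wrong direction | +0.47 | 57–78% |
| 0.8/0.2/0.2/0.8 | +0.27 | 74–98%, right direction | +0.47 | 56–77% |
| 0.5/−0.5/−0.5/0.5 | +0.48 | 99.5–100% | 0.00 | about 4% |

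Wrong-direction rates should be read against the 2.5% expected in one tail under no effect. The aligned difference is 0.48 and not 0.50 because the SD over both arms includes the group shift: 0.5/√(1 + 0.5²/4) = 0.5/1.031 = 0.485.

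As a check on the aligned column, the normal-approximation power for d = 0.5 with composite SDs 0.689, 0.791 and 0.880 (square roots of the variances above) is 0.80, 0.69 and 0.60.

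**Sensitivity of the uniform 0.5 case.** With 25 per arm: about 4% as written against 50–71% aligned. With 20 per arm: about 4% against 42–61%. With a ceiling on balance time that puts about 31% of controls at the cap: 4–5% against 57–78%.

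**The case against.** The strongest reply is that this is an omission and not a demonstrated error. The section is a short, past-tense summary. Reversing timed tests is an implementation step that such a summary may leave out, and the term cumulative score fits an aligned score as well. This stands as far as what was run: the documents do not show it either way. It does not rescue the definition, which gives the wrong quantity if followed literally.

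Second, the consequences are limited. The composite is secondary in a pilot, the ADLS gives a separate view of function, and no equivalence or non-inferiority test is set on the composite. The Potential Benefits text is not a decision rule. All of this is correct and limits the weight of the point.

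Third, the numbers rest on assumptions. The most extreme rows need a four-fold gap between the test pairs or opposite effects on them, and nothing in the documents supports either. The exact zero correlation with the aligned score also depends on equal correlations: if walk, stair and TUG correlate 0.7 with each other and 0.3 with balance, it is −0.8/√(2 × 10) = −0.18. That is still not a usable measure of function. The cancellation of a uniform effect needs no correlation assumption.

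Last, the near-zero remark could be meant to say that each arm's mean lies close to the overall mean, which would not be true by construction. The wording is unclear enough to allow that, but the statement about each subject is wrong on either reading.

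**Conclusion.** The point holds for the rule as written. The average has two positive and two negative components, so a uniform benefit or harm on all four tests has expected difference exactly zero. At an assumed 0.5 SD with 30 per arm, that means about 4% rejection where an aligned score would give 57–79%. With unequal effects, the size and sign depend on which pair of tests changes more, and the result can be understated, reversed or inflated. The percentages depend on the assumed effects, correlations and normality; the cancellation does not.

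Whether the reported analysis is affected cannot be settled from the documents. The primary outcome (ADLS divided by cost) and the ADLS, range-of-motion and cost analyses do not use this score. A smaller, separate point is that z-scores standardised on all subjects average zero by construction, so the plan's remark about near-zero averages says nothing about individual subjects or about direction.

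**What to change.** In the Statistical Analysis section, state the direction of each of the four tests, that the Stair Climb and TUG z-scores are multiplied by −1 before averaging, and that a higher composite means better function. State also which sample and visit supply the mean and SD for standardisation; all subjects at each visit is one workable choice, and the sign problem does not depend on it. Delete the sentence interpreting near-zero average z-scores, or replace it with the arm means if that is what was meant.

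If the signs were already aligned, say so and nothing need be rerun. If not, recompute the composite and its t-tests from the existing data. The cost is one or two sentences and at most that recomputation; no new data or patients are needed.

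### The sentence interpreting near-zero mean z-scores is an invalid inference, and the functional composite states no sign reversal for the two tests on which a lower score is better

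*Combined protocol and SAP*

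**What the plan says.** The Statistical Analysis section of the combined protocol and SAP says that "a z-score (or standard score) was used to calculate a cumulative score" from four tests: six-minute walk (distance), stair climb (time over number of steps), TUG (time) and balance on the surgical leg (time). It defines the composite thus: "The z scores are the average of the z scores for each of the functional tasks". It then comments: "On average, the z scores are close to zero, meaning that the overall individuals within the group". The conclusion it draws from this near-zero average is that "the scores for each subject are not different than the mean score across all subjects". The between-arm comparison follows: "Differences between the cumulative z-scores were assessed using a two-sample t-test". P-values below 0.05 "were considered statistically significant for all outcomes".

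Three things are not stated: the mean and SD used to form each z-score, whether the 5- and 10-week visits are standardised separately, and whether any test has its sign reversed before averaging. The same section names the ratio of ADLS to cost as the primary outcome, so this composite is secondary.

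**The concern.** The interpretive sentence treats an arithmetical property of z-scores as a finding. Standardised scores average zero over the sample they were standardised on, whether patients are alike or very different and whether or not the arms differ. A statement about each subject cannot be drawn from a mean.

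The composite itself is also incompletely defined. A patient who recovers well walks further and balances longer, which raises two z-scores, and climbs stairs and completes the TUG faster, which lowers the other two. If the four are averaged as they stand, a treatment that improves all of them moves the composite little or not at all. All four performance tests feed this one score, so a real difference in function could be missed, or even appear with the wrong sign.

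**Working it through.** **Inputs from the document.** Four tests and their units, the composite as a plain average, a two-sample t-test and a 0.05 threshold (Statistical Analysis). Arm size 30: "For the control group, 30 of these patients will undergo two to three weekly sessions", with 30 in the second group (Abstract, Methods).

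**Assumptions, not in the document.** Two-sided test; normal, complete data; the same true benefit δ (in SD units) on every test; equal correlation ρ between tests. The range is shown below.

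**Step 1: the plan's own figure, a mean close to zero.** For test j, z_ij = (x_ij − x̄_j)/s_j, with x̄_j and s_j taken over all n subjects. Then Σ_i z_ij = (Σ_i x_ij − n·x̄_j)/s_j = 0. The composite c_i = (z_i1 + z_i2 + z_i3 + z_i4)/4 therefore also averages 0. In simulation the overall mean stayed below 3 × 10⁻¹⁶ at δ = 0, 0.5, 1 and 2. With 10% of test values missing at random and δ = 1 it strayed by at most 0.07. The stated figure is reproduced, and it would be reproduced at any effect size.

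**Step 2: individual subjects.** With signs aligned and no arm difference, the composite has SD √((1 + 3ρ)/4). At ρ = 0.5 this is √0.625 = 0.79 (simulated 0.78, rising to 0.90 at δ = 2). About half of the subjects lie more than 0.5 from the mean. A zero mean is compatible with wide differences between patients.

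**Step 3: the arms, signs aligned.** With equal arms, the pooled SD of a test is √(1 + δ²/4), so the arm difference in z is δ/√(1 + δ²/4).
- δ = 0.8: 0.8/√1.16 = 0.8/1.077 = 0.74
- δ = 1: 1/√1.25 = 0.89, that is about ±0.45 per arm
- δ = 2: 2/√2 = 1.41, that is ±0.71 per arm

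The overall mean is zero throughout, yet the arms separate. At ρ = 0.5 the planned t-test rejected in 5%, 66%, 99.7% and 100% of runs at δ = 0, 0.5, 1 and 2. The test works as it should under pooled standardisation.

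**Step 4: the composite as written, no sign reversal.** Take δ = 0.8 in favour of one arm on every test. The shifts in z are +0.74 (walk), −0.74 (stair), −0.74 (TUG) and +0.74 (balance).
- As written: (0.74 − 0.74 − 0.74 + 0.74)/4 = 0
- With stair and TUG reversed: (4 × 0.74)/4 = 0.74

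Simulated rejection rates, 30 per arm:

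| True benefit on every test | ρ | Signs aligned | As written |
|---|---|---|---|
| 0.5 SD | 0.5 | 66% | 4% |
| 0.8 SD | 0.2 to 0.6 | 99.7% down to 95% | about 3% |
| 1 SD | 0.5 | 99.7% | 2% |

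Cancellation is complete only for a uniform benefit. If the 0.8 SD benefit fell on stair climb and TUG alone, and pooled z-scores were averaged unreversed, the expected difference would be (0 − 0.74 − 0.74 + 0)/4 = −0.37. That has the opposite sign to the same average with higher taken as better.

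**The case against.** The strongest reply is that the comparison of arms does not use the interpretive sentence at all. The next sentence names a two-sample t-test, and Step 3 shows that it performs normally. That stands. A reader might infer that the plan is bound to find no difference whatever the data; the document does not support this. Nor does the sentence say the arms are equal. It compares subjects with an overall mean, so it cannot be read as a declared finding of equivalence between interACTION and control.

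A reader might also infer, from the reference to individuals within the group, that scores are standardised inside each arm, which would force both arm means to zero and disable the t-test. The text does not say so, and the only reference mean it names is the one across all subjects, which points to pooling. Conversely, if the phrase refers to an arm average under pooled standardisation, that average is free to move and is informative about the arm. Even then it says nothing about each subject.

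On signs, the reply is that reversing timed tests is routine and may have been done without being written down. That is possible, since silence does not prove omission. But the section gives each test's unit and the averaging rule, and a programmer following it literally would not reverse anything.

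Separate standardisation at each visit is not an error. The plan specifies no change-over-time analysis for this composite, and the between-arm contrast at each visit is kept.

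**Conclusion.** The point holds in two parts. First, the interpretive sentence is wrong under any standardisation: with z-scores formed on all subjects the near-zero overall mean is an identity, and no mean can show that each subject equals it. This part is algebra and rests on no assumed effect size. It does not invalidate the planned t-test.

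Second, the composite as written combines tests scored in opposite directions. Read literally, rejection falls to about 3% from 95% to 99.7% with aligned signs. That size rests on a 0.8 SD benefit on every test, ρ between 0.2 and 0.6, 30 per arm and a two-sided 0.05 level, and on no reversal having been applied, which the document leaves open. With unequal benefits the cancellation is partial and the direction may be misleading.

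The correction is worth making because the error is definite and the remedy nearly free. Its weight is limited because this is a secondary outcome.

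**What to change.** In the Statistical Analysis section:

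1. Delete the sentence that interprets the near-zero average.
2. State that each test is standardised with the mean and SD of both arms combined, and say whether this is done per visit or across visits.
3. State that the stair climb and TUG z-scores are multiplied by −1 before averaging, so that a higher composite always means better function.
4. Base the conclusion on the between-arm difference in the composite with its 95% CI, alongside the planned t-test.

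If the composite has already been computed, check the code for the sign convention and recompute if no reversal was made. The cost is a few lines of SAP text and code, with no new data and no change to trial conduct.
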